5.4. Instructions for Use

The Scorpion sets will be used in accordance with current Instructions for Use (IFU) included in the device packaging. The manufacturer's IFU for each Portal Vein Access Set contains the following information:

- Complete instructions including storage and handling requirements, preparation for use, pre-use checks, precautions to be taken after use, and disposal.
- Complete summary of the necessary training and experience required for use of these devices.
- Complete description of the procedures involved in the use of these devices.

The Scorpion Portal Vein Access Set are identified with part number and lot number.

Table 2. Scorpion Portal Vein Access Kit Part Numbers

Part Number	Description
TPS005	Scorpion® Portal Vein Access Set
TPS006	Scorpion®X Portal Vein Access Set

All components of the Scorpion set are supplied sterile and are intended for single use only. The devices must not be re-sterilized.

6. RISK ANALYSIS AND RISK ASSESSMENT

6.1. Anticipated Benefits

Safe and effective creation of parenchymal tract between the hepatic vein and an intrahepatic branch of the portal vein.

6.2. Risks and Foreseeable Adverse Events and Adverse Device Effects

The following foreseeable adverse events, which are captured in the IFU of these commercially available devices, may be considered as potential risks to patients undergoing TIPS procedures with an Argon Portal Vein Access Set:

- Intraperitoneal hemorrhage or hemoperitoneum
- Puncture site hematoma
- Cardiac arrhythmia
- Cardiac tamponade
- Arteriovenous fistula or other arterial injury
- Arterio-biliary fistula or biliary tract injury
- Extrahepatic Organ Injury
- Capsular Perforation
- Needle/catheter/guidewire fracture
- Foreign body retention

There is no additional risk associated with this clinical study since the patient was treated according to standard of care.

7. STUDY OBJECTIVE

The objective of this retrospective data collection is to evaluate the safety and effectiveness of Scorpion portal vein access sets during TIPS with the goal of creating the parenchymal tract for indicated interventional procedures.

7.1. Outcome Measurements

The data collected will be used to analyze the following outcome measures:

7.1.1. Primary Outcome

- a. Technical success defined as creation of the parenchymal tract between the hepatic vein and an intrahepatic branch of the portal vein and confirmed by portogram

7.1.2. Secondary Outcomes

- a. Procedural success defined as successful delivery of the shunt
- b. Incidence of procedural complications defined as the total occurrence of complications

8. STUDY DESIGN**8.1. Overview**

The planned sample size is to enroll at least 50 eligible cases at a single center in the United States. Clinical data will be retrospectively collected on eligible cases that underwent attempted TIPS procedures with one of Argon's standard Portal Vein Access Set between February 1, 2022 and February 29, 2024.

The participating center will be identified by a site number, and eligible cases will be sequentially assigned a unique 3-digit study identification (ID) number. The ID number will be a combination of the site number followed by a 2-digit number sequentially assigned based on eligibility (e.g. 101, 102, 103).

8.2. Eligibility Criteria**8.2.1. Inclusion Criteria**

1. Scorpion or Scorpion X kit introduced into the vasculature as the initial device for portal vein access

8.2.2. Exclusion Criteria

1. TIPS procedure was not initiated and/or no portion of the kit was introduced into the vasculature
2. Inaccessible medical records

9. STUDY ENDPOINTS**9.1. Primary Endpoints**

The primary effectiveness endpoint is technical success defined as creation of the parenchymal tract between the hepatic vein and an intrahepatic branch of the portal vein and confirmed by portogram (CO₂/contrast).

The primary safety endpoint is a composite of major complications associated with the procedure or study device and defined as complications resulting in an unplanned increase in the level of care, prolonged hospitalization, permanent adverse sequelae, or death.¹⁰

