3. SYNOPSIS

Protocol SCPVA02	
Title	A Retrospective Study to Assess the Safety and Efficacy of Scorpion for Transjugular Intrahepatic Portosystemic Shunt (TIPS) Procedures
Short title	Achieving Portal Access with Scorpion Post-Approval Study 2 (APASS2)
Protocol Number	SCPVA02
Study Device	
Name	Scorpion® Portal Vein Access Set Scorpion®X Portal Vein Access Set
Intended Use	The Scorpion and Scorpion X Portal Vein Access Sets are intended for transjugular liver access in diagnostic and interventional procedures.
Sponsor	
Name	Argon Medical Devices Inc.
Contact Details	[name] [contact] [contact]
Investigational Sites	
Number of Sites	1 site
Location of Sites	United States (US)
Clinical Study Design	
Design	Retrospective, single center, single arm design.
Objective	To evaluate the safety and effectiveness of Scorpion Portal Vein Access Kits for TIPS procedures with the goal of creating the parenchymal tract for indicated interventional procedures. Safety, effectiveness, and performance data for the Scorpion Portal Vein Access sets will be collected
Hypothesis	No formal statistical hypothesis will be tested
Primary Effectiveness Endpoint	Technical success, which is defined as creation of the parenchymal tract between the hepatic vein and an intrahepatic branch of the portal vein confirmed by portogram (CO ₂ /contrast)
Primary Safety Endpoint	Major complications associated with the device/procedure, which are defined as complications resulting in an unplanned increase in the level of care, prolonged hospitalization, permanent adverse sequelae, or death
Secondary Endpoints	
 • Procedural success defined as successful delivery of the shunt • Device-Related Complications, in the judgment of the Principal Investigator

Exploratory Endpoints 
 • Portal vein access (PVA) time defined as the time from hepatic vein access to portal vein access • Procedure duration defined as the interval from the first jugular access for TIPS creation to removal of catheters from the subject • Fluoroscopy Time • Change in Model for End-Stage Liver Disease (MELD) and Child-Pugh score • Radiation dosage measured in Air kerma (mGy) • Contrast volume used • Length of hospital stay and number of ICU days • Change in hepatic venous pressure gradient (HPVG) 	
Clinical Study Population	

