Population	
All patients who underwent a TIPS procedure between February 1, 2022, and February 29, 2024 will be considered for enrollment in the study. Procedural data will be collected from patient medical records through hospital discharge.
 
Each TIPS procedure that was completed using one of the Scorpion Portal Vein Access Kits will be considered as an individual case. Cases that meet all inclusion criteria and do not meet any exclusion criteria will be considered eligible for enrollment.

Inclusion Criteria	
 1. Scorpion or Scorpion X kit introduced into the vasculature as the initial device for portal vein access.
Exclusion Criteria	
 1. TIPS procedure was not initiated and/or no portion of the kit was introduced into the vasculature. 2. Inaccessible medical records.
Statistical Analysis	
Statistical Methodology	
Patient demographics and performance parameters will be summarized with mean, standard deviation, median, and range for continuous variables and with frequencies and percentages for discrete variables. Sub-group analysis will be conducted when sample size permits.

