10.2. Patient Selection

Electronic Medical Records (EMR) will be used to identify patients who underwent a TIPS procedure using Scorpion® Portal Vein Access Set or Scorpion®X Portal Vein Access Set with standard techniques from February 1, 2022, through February 29, 2024, by searching for Current Procedural Terminology (CPT) codes 37182 and 37183 within the study period.

Suitable cases identified during the study period will be evaluated for eligibility. Eligible cases will be assigned a sequential 3-digit number as the case ID. Each TIPS procedure attempt will be considered as an individual case with different case ID. The patient log will be retained at the site and filed with the study records at the conclusion of the study.

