12.3. Analysis Population

Due to the nature of this retrospective study, all eligible cases will be analyzed for safety and effectiveness on an 'as-treated' basis.

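### Technical success names no device, so a tract made by a non-Scorpion set after a switch can count for Scorpion, and the synopsis's case definition can instead drop such cases from the denominator.

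*Combined protocol and SAP*

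**What the plan says.** The endpoint is defined in three places, each time without a device.

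- Section 3 (Synopsis): "Technical success, which is defined as creation of the parenchymal tract between the hepatic vein and an intrahepatic branch of the portal vein", confirmed by CO₂ or contrast portogram.
- Section 7.1.1: "creation of the parenchymal tract between the hepatic vein and an intrahepatic branch of the portal vein and confirmed by portogram".
- Section 9.1: "technical success defined as creation of the parenchymal tract between the hepatic vein and an intrahepatic branch of the portal vein", again with portogram confirmation.

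Who is counted is described in several places, and they do not agree.

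- Section 8.2.1, repeated in the synopsis, has one inclusion criterion: "Scorpion or Scorpion X kit introduced into the vasculature as the initial device for portal vein access".
- Section 8.2.2 excludes only procedures that were not initiated or in which no part of the kit entered the vasculature, and cases with inaccessible records.
- Section 3, Population: "Each TIPS procedure that was completed using one of the Scorpion Portal Vein Access Kits will be considered as an individual case".
- Section 8.1 speaks of "eligible cases that underwent attempted TIPS procedures with one of Argon's standard Portal Vein Access Set".
- Section 10.2: "Each TIPS procedure attempt will be considered as an individual case with different case ID".
- Section 12.3: "all eligible cases will be analyzed for safety and effectiveness on an 'as-treated' basis".

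On data capture, Section 10.3 asks for the primary Argon device. Section 10.3.2 lists which of the two Scorpion sets was used, in a list introduced as illustrative. Neither asks about a non-Scorpion set. Section 11.2 restricts adverse-event collection to procedure-related complications.

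**The concern.** Section 7 sets out to evaluate the Scorpion sets. For an access set, having to reach for another set to make the tract is a plain form of ineffectiveness. The plan does not say how to score it. Read literally, it is a success. Under the synopsis's case definition it may not be counted at all.

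The percentage carries weight. Section 4.3 says that the study will supply clinical data for the initial CE Mark application and show that the sets meet the sponsor's acceptance criteria. There is no comparator and no hypothesis test, and Section 12.4 plans frequencies and percentages. The technical success percentage is therefore itself the effectiveness result, and a reader will take it as a property of the Scorpion sets.

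**Working it through.** **Step 1: follow a switched case through the plan.** Take a procedure in which a Scorpion kit is introduced first, the operator changes to a non-Scorpion set, that set makes the tract, and a portogram confirms it.

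- Inclusion (8.2.1): met, because Scorpion was the initial device.
- Exclusions (8.2.2): neither applies.
- Analysis population (12.3): included as an eligible case. 'As-treated' has no stated meaning in a single arm and gives no rule for a switch.
- Endpoint (3, 7.1.1, 9.1): met. The portogram confirms the tract, not the tool that made it.
- Synopsis case definition: arguably not met, since a Scorpion kit did not complete the procedure. The attempt-based wording of 8.1 and 10.2 points the other way.

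**Step 2: the rates under each rule.** The plan has no sample size calculation or target rate to reproduce. N = 50 is the anticipated minimum (Section 12.2). The other counts are assumptions: *s* switches, of which *r* are rescued (the other set makes the tract), and *f* further attempts that end with no tract.

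- Switch scored as device failure: (N − s − f)/N
- Literal reading: (N − (s − r) − f)/N
- 'Completed using', only switched cases leave: (N − s − f)/(N − s)
- 'Completed using', attempts with no tract leave too: (N − s − f)/(N − s − f) = 100%

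**Step 3: direction.** Literal minus device-failure is r/N, which is never negative. At N = 50 it is 1/50 = 2 percentage points per rescued switch; with more cases it is less. The 'completed using' rules keep the device-failure numerator and use a denominator no larger than N, so they cannot give a lower rate.

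**Step 4: illustrations.** Exact (Clopper-Pearson) 95% intervals are added for scale; the plan does not call for them.

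*Three switches, no other failure (s = 3, f = 0):*

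| Rule | Result | 95% interval |
|---|---|---|
| Device failure | 47/50 = 94% | 83.5–98.7 |
| Literal, r = 3 | 50/50 = 100% | 92.9–100 |
| Literal, r = 2 | 49/50 = 98% | 89.4–99.9 |
| Literal, r = 1 | 48/50 = 96% | 86.3–99.5 |
| Literal, r = 0 | 47/50 = 94% | 83.5–98.7 |
| 'Completed using' | 47/47 = 100% | 92.5–100 |

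*Three rescued switches and two attempts with no tract (s = r = 3, f = 2):*

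| Rule | Result | 95% interval |
|---|---|---|
| Device failure | 45/50 = 90% | 78.2–96.7 |
| Literal | 48/50 = 96% | 86.3–99.5 |
| 'Completed using', switches leave | 45/47 = 95.7% | 85.5–99.5 |
| 'Completed using', no-tract attempts leave too | 45/45 = 100% | 92.1–100 |

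*No switch, two attempts with no tract (s = 0, f = 2):* the device-failure and literal rules both give 48/50 = 96%. If the no-tract attempts leave, the rate is 48/48 = 100%. The case-definition conflict therefore matters even without a switch.

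**The case against.** **The literal reading is contested.** The synopsis wording can be read to say that a switched procedure is not a case, so it is too strong to say that such a case certainly counts as a success. That stands as a limit. The literal reading is still the stronger one: the same synopsis paragraph makes eligibility turn on the inclusion and exclusion criteria, and the inclusion criterion is initial use. The alternative does not score the switch as a failure either; it removes the case.

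**The intent is clear from the objective.** A reader could infer from Section 7 that a switch is a device failure. No section says so, and an abstractor filling in the technical success item would be working from the definition.

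**A switch might be recorded anyway.** The lists in Sections 10.3 and 10.3.2 are open-ended, and the procedure records will be reviewed. This stands in part: capture is possible but not required. It is tempting to conclude from Section 11.2 that the study database would hold no trace of an uncomplicated switch. The section does not support that, because it limits which adverse events are collected and not the database as a whole. It shows only that the adverse-event route would not pick such a switch up.

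**Switches may be rare or absent.** Section 4.2 cites a retrospective series of 15 Scorpion X cases with 100% technical success. The exact lower 95% limit for 15/15 is 0.025^(1/15) = 78.2%, and the plan does not say how that series defined success. It neither supports nor rules out the counts assumed above.

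**Scoring every switch as failure is one choice among several.** Reporting tract creation both overall and by Scorpion alone would also serve the objective. That is fair, and the fix leaves room for it.

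**Conclusion.** The point holds, as something that should be fixed. As written, the plan can credit another set's tract to Scorpion or, under the synopsis wording, drop the case. Relative to scoring a switch as a device failure, both routes leave the primary percentage unchanged or raise it. The literal reading adds 2 points per rescued switch at N = 50 and nothing for a switch that ends without a tract.

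The size rests on assumed counts, because the documents give no switch rate. With no switch the device-attribution bias is zero, but the case-definition conflict can still raise the rate if attempts with no tract are dropped.

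A reader might infer that the reported rate will in fact be inflated, or that the device would miss its acceptance criteria under a stricter rule. The documents support neither: they do not show that any switch occurred, they state no numeric criterion, and no hypothesis is tested.

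**What to change.** 1. In Sections 3, 7.1.1 and 9.1, define technical success as a portogram-confirmed tract created with the Scorpion or Scorpion X puncture tool. State that a case whose tract was made by a non-Scorpion set stays in the denominator as a technical failure. Section 5.1 identifies the puncture tool as the part that makes the pathway, so use of the compatible introducer set named there would not count as a switch. Tract creation by any device may be reported as a supplementary figure.
2. Reconcile the synopsis's case definition with the attempt-based wording in Sections 8.1 and 10.2. In Section 12.3, replace 'as-treated' with an explicit denominator: all eligible cases in which a Scorpion or Scorpion X kit was introduced as the initial device.
3. Add an item to Section 10.3.2 recording whether another portal vein access set was used and which set made the tract.

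The cost is a wording amendment and one more chart-review item. If abstraction has begun, which the documents do not say, that item means going back to the procedure records. The reported rate may be slightly lower if switches occurred. If none did, the item lets the sponsor show that the rate belongs to Scorpion.

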9.2. Secondary and Exploratory Endpoints

The secondary and exploratory endpoints of this clinical study are outlined in **Table 3**.

Table 3. Overview of Secondary and Exploratory Endpoints

Endpoint	Description / Definition
Secondary Endpoints	
Procedural success	Successful delivery of the shunt
Device-related complications	Incidence of complications related to the device as judged by the Principal Investigator
Exploratory Endpoints	
Portal Vein Access (PVA) time	Time (in minutes) from hepatic vein access to portal vein access
Procedure duration	Interval (in minutes) from first jugular access for TIPS creation to removal of catheters from subject
Fluoroscopy time	Measured in minutes
Change in MELD score Change in Child-Pugh score	Change in score from Baseline Characteristics to Follow Up Data
Radiation dosage	Measured in air kerma (mGy)
Contrast volume used	Measured in mL
Length of Hospital Stay	Measured in days
Number of ICU days	Measured in days
Change in HPVG	Measured in mm Hg

MELD = Model for End-Stage Liver Disease; ICU = Intensive Care Unit; HPVG = Hepatic Venous Pressure Gradient

10. STUDY PROCEDURES

10.1. Informed Consent

Since the data for this retrospective review already exists, we request that the IRB waive the consent requirement. Any patient who has previously refused to participate in a study will not have his or her data included in the study. The data will be de-identified and no personal identifying information will be disclosed or compromised.

10.2. Patient Selection

Electronic Medical Records (EMR) will be used to identify patients who underwent a TIPS procedure using Scorpion® Portal Vein Access Set or Scorpion®X Portal Vein Access Set with standard techniques from February 1, 2022, through February 29, 2024, by searching for Current Procedural Terminology (CPT) codes 37182 and 37183 within the study period.

Suitable cases identified during the study period will be evaluated for eligibility. Eligible cases will be assigned a sequential 3-digit number as the case ID. Each TIPS procedure attempt will be considered as an individual case with different case ID. The patient log will be retained at the site and filed with the study records at the conclusion of the study.

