5.3. Device Identification and Tracking

As commercially available devices, Scorpion® Portal Vein Access Set and Scorpion®X Portal Vein Access Set were obtained by the site through normal commercial procurement methods and stored and accounted for following site-specific policies.

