12.2. Sample Size Determination

No formal sample size calculation was performed. All eligible cases will be enrolled in the study. Per preliminary estimation and historical sales report, we anticipate that there will be at least 50 cases for this study at 1 clinical site in the US.

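### Cases are found only through two procedure codes, so an abandoned attempt carrying neither code would not be screened and success may be overstated

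*Combined protocol and SAP*

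**What the plan says.** Section 10.2 describes one way into the study: an EMR search for patients who had TIPS with a Scorpion set, carried out "by searching for Current Procedural Terminology (CPT) codes 37182 and 37183 within the study period". Cases found this way are then checked for eligibility. The EMR and PACS review in 10.3 comes later and extracts data on cases already judged eligible.

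The intended population is attempts. Section 8.1 refers to "eligible cases that underwent attempted TIPS procedures with one of Argon's standard Portal Vein Access Set". Section 10.2 adds: "Each TIPS procedure attempt will be considered as an individual case with different case ID". The single inclusion criterion in 8.2.1 is "Scorpion or Scorpion X kit introduced into the vasculature as the initial device for portal vein access". The exclusions in 8.2.2 remove only procedures not started or without a kit introduced, and cases with inaccessible records. Section 12.2 commits to enrolling every eligible case.

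The synopsis population differs: "Each TIPS procedure that was completed using one of the Scorpion Portal Vein Access Kits will be considered as an individual case".

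Two other sources are mentioned, neither for case finding. Section 5.3 says kits were "stored and accounted for following site-specific policies". Section 12.2 uses sales only to forecast numbers: "Per preliminary estimation and historical sales report, we anticipate that there will be at least 50 cases".

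**The concern.** Whether a case is found may depend on its outcome. If a kit was introduced, the portal vein was not reached and the procedure was stopped, no shunt was placed. The case may then carry a different code or none. It is eligible under 8.2, but the search would not return it.

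That case fails the primary effectiveness endpoint (tract confirmed on portogram) and the procedural success endpoint (shunt delivered). If it is missed, it drops out of the denominator and the success rate rises. If missed attempts had major complications more often than found ones, the primary safety rate would be too low.

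The study has one arm and tests no hypothesis (12.4), so its main output is these proportions. Section 4.3 says they will support an initial CE Mark application and be set against acceptance criteria that the protocol does not state. No analysis of the coded cases can reveal the ones that were never listed.

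**Working it through.** **The plan's own figure.** There is no calculation to reproduce. The figure of at least 50 cases is a feasibility forecast, and 12.2 says no formal sample size calculation was done.

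**Which attempts are exposed.** Setting 8.2 and 9 beside the search in 10.2:

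| Attempt with Scorpion as initial device | Eligible under 8.2 | Reached by the code search | Effect if missed |
|---|---|---|---|
| TIPS completed | Yes | Yes, assuming completed TIPS carries one of the codes | – |
| Scorpion fails, another kit completes TIPS in the same session | Yes | Probably, since it ends as a TIPS | – |
| Attempt abandoned, patient has a later coded TIPS in the window | Yes | Probably, since the patient is found and the chart can be screened | – |
| Tract confirmed, stopped before shunt delivery | Yes | Not stated | Inflates procedural success only |
| Stopped before portal vein access, no coded TIPS in the window | Yes | Only if the site gives it one of the two codes | Inflates technical and procedural success |

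The last row is the group at risk for the primary endpoint.

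**Illustration 1: a few missed failures.** Assume the search finds n = 50 cases (the forecast in 12.2), all technical successes, and misses m failures. The documents do not give m. The full-series rate is 50/(50 + m). Intervals are exact (Clopper-Pearson) 95%; when all n cases succeed, the lower limit is 0.025^(1/n), here 0.025^(1/50) = 0.929.

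| m | Rate | Exact 95% CI |
|---|---|---|
| 0 (as reported) | 50/50 = 100% | 92.9 to 100 |
| 1 | 50/51 = 98.0% | 89.6 to 100.0 |
| 2 | 50/52 = 96.2% | 86.8 to 99.5 |
| 3 | 50/53 = 94.3% | 84.3 to 98.8 |
| 5 | 50/55 = 90.9% | 80.0 to 97.0 |

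If one failure is already among the 50, the reported 49/50 = 98.0% (89.4 to 99.9) becomes 49/52 = 94.2% (84.1 to 98.8) with two missed.

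**Illustration 2: partial capture.** Let p be true technical success and c the share of failed attempts that the search finds, with all successes found. The expected observed rate is p / (p + (1 − p)c). For p = 0.95 and c = 0.5 this is 0.95/(0.95 + 0.025) = 0.974, an upward bias of 2.4 percentage points. Bias in points:

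| p | c = 1 | c = 0.75 | c = 0.5 | c = 0.25 | c = 0 |
|---|---|---|---|---|---|
| 0.90 | 0 | 2.3 | 4.7 | 7.3 | 10.0 |
| 0.95 | 0 | 1.2 | 2.4 | 3.7 | 5.0 |
| 0.98 | 0 | 0.5 | 1.0 | 1.5 | 2.0 |

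Both p and c are assumptions; the documents give neither for this site. The bias is zero if every failed attempt carries one of the codes, or if there are no failures.

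**The case against.** A reader might infer that the series is in fact enriched for successes. The documents do not support that. They define neither code and do not say how this site codes an abandoned attempt. If it uses the same two codes, nothing is lost.

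The exposed group is also narrower than all failures, as the first table shows: rescues in the same session, and patients with a later coded TIPS, would probably be found. Illustration 1 is the extreme case, with every found case a success and every missed case a failure. The only earlier Scorpion results cited (4.2) are 100% technical success in 15 Scorpion X cases and 100% procedural success in a three-case study that included two Scorpion cases, so failures may be few. No numerical threshold is stated, so no decision can be shown to change.

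A reader might also take 5.3 as proof that a full usage log exists, and treat every unmatched kit as a failed attempt. Neither follows. Section 5.3 describes no patient-level log. Under 5.2 the sets are for diagnostic as well as interventional liver access, so an unmatched kit may have been used outside TIPS. It may never have been introduced (excluded by 8.2.2) or may have been a second device (not eligible under 8.2.1). The unit of analysis in 12.4 is the procedure, not the kit.

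These points limit the claim to a possible bias of unknown size. They do not remove it: the protocol leaves the coding question open and plans no check that would answer it.

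**Conclusion.** The point holds as a risk. The only case-finding route may miss attempts abandoned before portal vein access that carry neither code, in patients without a coded TIPS in the window. Those attempts are eligible and count as failures. Technical and procedural success may therefore be biased upward. The effect on major complications is less certain, because it depends on how often the missed attempts had one.

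The size cannot be determined from the documents. On the assumption of 50 found cases, all successes, one to five missed failures would lower the rate by 2.0 to 9.1 points (100 − 98.0 and 100 − 90.9). Over the ranges in Illustration 2 the bias runs from 0 to 10 points. These figures show sensitivity and are not estimates. The conflict between completed procedures in the synopsis and attempts in 8.1 and 10.2 is a plain inconsistency, and it makes the risk worse: an attempt recovered from another source could still be left out under the synopsis definition. This is an inexpensive improvement that the sponsor should make.

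**What to change.** In 10.2, keep the code search and build the candidate list as its union with:

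- the interventional radiology procedure log (or PACS), and
- where the site holds them, kit-use or charge records for part numbers TPS005 and TPS006,

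all for 1 February 2022 to 29 February 2024. Screen every attempt identified against 8.2.

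Report a flow showing attempts found by each source, enrolled, and excluded with reason, together with the number of kits not accounted for. Do not count those kits as failures in the main estimate. Give their number and, at most, one clearly labelled worst-case bound.

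Reconcile the synopsis population with 8.1 and 10.2 so that all three refer to attempts, in line with the eligibility criteria in 8.2.

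Cost: one or two extra record queries and a reconciliation by the same staff, at one site and over a closed window. The success rate may come out slightly less favourable. If no uncoded attempts turn up, the sponsor has evidence that the series is complete.
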